3. METHODOLOGY

Study Design: The study is a Phase 2 randomized controlled, partial-blind, parallel group study in plasmodium infected *asymptomatic* adults 18 years and older, with 8 study arms. It will use the adapted Zelen design. The adapted Zelen design uses two steps in the consent process. In the first step, there is an informed consent from all participants for a cohort lifestyle study. After consent is obtained, baseline assessment and screening will be performed, and eligible participants randomly assigned to the different study arms. According to this consent, participants are randomized without knowledge about the detailed protocol. In the second step, only participants from the intervention group will receive the information about the intervention and the second consent will be obtained from them. The participants who will decline to participate to an intervention will continue in the cohort study, as the control group.

Duration of study: The study duration is 35 days (5 weeks) for each participant.

Treatment groups (TG):

TG 1: Group of 8 persons receiving *A. afra* infusions of 5g/1liter of water, 3drinks a day, daily for 1week (7 days) (current recommendation).

TG 2: Group of 8 persons receiving *A. afra* infusions of 5g/500ml of water, 2drinks a day, daily for 1week (7 days) (increase concentration and decrease dose frequency).

TG 3: Group of 8 persons receiving *A. afra* infusions,5g/1liter of water 3drinks a day, weekly for 4weeks (decrease dose frequency and increase length of treatment).

TG 4: Group of 8 persons receiving flavored *A. afra* infusions, 5g/1liter of water 3drinks a day, daily for1week (7 days) (current treatment with improved taste).

TG 5: Group of 8 persons flavored *A. afra* infusions, 5g/500ml of water 2drinks a day, daily for 1 week (7 days) (improved taste, increase concentration and decrease dose frequency).

- **TG 6:** Group of 8 persons receiving flavored *A. afra* infusions, 5g/1liter of water 3drinks a day, weekly for 4weeks (improved taste, decrease dose frequency and increase length of treatment);
- **TG 7**: Group of 4 persons receiving flavored placebo infusions, 5g/liter of water 3drinks a day, daily for 1week (7 days) (improved taste with no active molecule);
- **TG 8**: Group of 4 participants receiving regular tea placebo taken as desired, daily for 1 week (7 days) (Regular tea with no active molecule).

[figure not shown]

Figure 2. Screening and recruitment of study participants

Rapid diagnostic test (RDT), Positive (Pos) Negative (Neg), Real time Polymerase Chain reaction (rt-PCR), Quantitative Polymerase Chain reaction (qPCR)

[figure not shown]

Figure 3. Algorithm to find the activity level, optimal dosage, and accepted formulation of *Artemisia afra* in eliminating plasmodium reservoirs.

Study description:

Study population: The trial will be conducted among Plasmodium infected asymptomatic students and workers in the University of Buea -Cameroon and the Rwanada National University (UR. Fifty-six positive participants have to be enrolled per site, making 112 participants in the whole study. To reach the required number of gametocyte carriers, 635 persons will be RDT tested in Buea (South-west region) where the expected positive RDT was 9.8% in Demographic health survey (DHS) 2018 (34) and drop-

out rate was set at 10%. In Kigali where the expected positive RDT was 14.4% in Malaria indicator survey (MIS)2017 (35) and drop-out rate was set at 10%, hence 432 persons will be RDT tested to reach the required number of gametocyte carriers.

This study will use the adapted Zelen design which has two steps in the consent process. At step one, informed individuals (students and workers) will be invited to participate in a screening and cohort survey on asymptomatic malaria, aimed at understanding the comportment of plasmodium parasite in asymptomatic plasmodium carriers over time. After informed consent is obtained during the first encounter (day 0), baseline assessments will be done and sociodemographic variables, clinical/medical history, physical assessment, prior medications information and participants' contact details will be recorded. Blood samples will be collected from each participant and examined for the presence of parasites (Gametocytes) using malaria rapid diagnostic test kit (mRDT). RDT positive samples will be re-examined with qPCR (quantitative polymerase chain reaction) and direct microscopy for confirmation. The qCPR will be repeated for negative samples and participants excluded if still negative. All qPCR positive samples will be further analyzed with rt PCR (real time polymerase chain reaction), for parasite quantification and specific stage identification, targeting specific parts of the gametocyte genes. Participants who fulfil the inclusion criteria will be randomly allocated in the 8 study arms in a 2:2:2: 2:2:2: 1:1 ratio for the 6 treatment and 2 control arms, respectively. In the second step, only participants from the intervention groups (TG1- to -TG7) will receive the information about the intervention and a second consent will be obtained from them. Treatment administration will be based on the allocation arm. The treatments will consist of Artemisia afra tea infusions for the 6 trial arms versus favored placebo infusions and desired regular tea for the 2 control arms. The participants who will decline to participate to an intervention will continue in the cohort study, as a control group on regular tea (TG 8).

Screening and recruitment: Screening will be done during at baseline visit (Day 0) in the health stations set up in the study sites. After informed consent is obtained, baseline assessments will be performed to obtain information on sociodemographic characteristics, clinical/medical history, physical assessment, prior medications, and participants' contact details. This will be followed by screening tests for presence of plasmodium parasites. Participants who fulfil the inclusion criteria will be enrolled in the study.

Randomization: Prior to treatment, eligible participants will be randomly assigned into the 8 study arms. The randomization method will be a permuted block randomization, with a block size of either 14 or 28 at random, and with a two-to-one allocation ratio for each active arm against two different control arms (2:2:2:2:2:1:1).

Blinding: The participants in the intervention arms will be aware of their assignment to an intervention group but unaware of the treatment assigned to them. The site staff (investigators or observers) will be

aware of assignments to one control arm (regular tea group), but unaware of assignments in the other treatment arms.

Visits/assessment schedules: A total of five study visits will be effected, being one baseline visit on Day 0, and four follow-up visits on Day 7, 14, 28 and 35, from baseline. During the baseline visit plasmodium tests targeting specific parts of the gametocyte genes will be done to determine the participants' initial (baseline) parasite load, and during subsequent visits, follow up control tests (rtPCR and blood smear) will be done, and the gametocyte load recorded, alongside assessments for clinical symptoms and adverse sides effects (if any).

Endpoints The efficacy of each of the treatment dosage schedule will be evaluated on day 7,14,28 and 35 from baseline, based on response to treatment or reservoir elimination rate. Response to treatment will be indicated by an absolute increase in Cycle threshold (Ct >20), or a negative rt-PCR tests results (Ct >40). If the patient misses the follow-up visit, compliance will be noted in the completion worksheet (filled out at end of study) and the parasite load and adverse side effects noted during the last visit considered. No severe side adverse effects are expected from the treatment but since toxicity is always a concern in clinical trials involving humans, participants will be observed for any severe ASEs and withdrawal noted throughout the study duration.

Clinical symptoms (mild malaria symptoms): That may occur during the trial period will be assessed daily by site (observing) staff and recorded in the home or site visit worksheets at Visit Day 7, 14,28, and 35 including Temperature > 37°C, Chills (Perspiration), Sweats, Headaches, nausea and vomiting, body aches, general malaise (Weakness), enlarged spleen, mild jaundice, enlargement of the liver, and increased respiratory rate (>20 /min). Participants with confirmed malaria symptoms will be treated with the WHO recommended treatment for symptomatic malaria.

Data collection: Data will be captured through the Observation worksheet and entered in Electronic Case Report Forms (eCRF), by interviewing the participants during observation, reviewing available medical records, and documenting assessment records.

Written informed consent will be obtained before conducting any study related procedures or treatment on the participants. Participants will first be informed about the aim of the study, designs, potential gain, and their right to stop at any moment if they accept to enter the study. Then they will be requested to sign a written informed consent.

Ethical considerations: Administrative authorization will be obtained from the ministry of public health in Cameroon and Rwanda, and administrative authorities of the various study sites. Ethical authorization will be obtained from the Faculty of Health science Institutional Review Board (FHSIRB) of the University of Buea, Cameroon and the Rwandan National Ethical Committee (RNEC). All study participants will have a clear and detailed explanations about the study and requested to freely sign a written informed consent.

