designs, potential gain, and their right to stop at any moment if they accept to enter the study. Then they will be requested to sign a written informed consent. Number of study Fifty-six positive participants have to be enrolled per site, making 112 participants in the whole participants: study. To reach the required number of gametocyte carriers, 635 persons will be RDT tested in Buea (Southwest region) where the expected positive RDT was 9.8.% in Demographic health survey (DHS) 2018 and drop-out rate was set at 10%. In Huye (South region), the expected positive RDT was 14.4% in Malaria indicator survey (MIS)2017 and drop-out rate was set at 10%, hence 432 persons will be RDT tested to reach the required number of gametocyte carriers. Study All students and staff members of the University will be invited to participate in the study. population Participants will be included in the study if in good health (based on physical examination and /Participants medical history), and if they meet all specified eligibility criteria. characteristics/ Inclusion criteria for trial allocation groups Study sites/ Asymptomatic Plasmodium positive students or workers from the selected study universities, aged 18 years and above who provide written informed consent. **Exclusion criteria for trial allocation groups** 1. To have a known hypersensitivity to any ingredients of the tea. 2. Currently taking any malaria drug for prevention or treatment. 3. To have participated in another malaria drug trial or device in the last 1month. 4. To have a history or presence of clinically significant medical, psychiatric, or emotional condition. The study will be conducted at the University of Buea in Cameroon, and the University of Rwanda. All students and staff members of the University will be invited to participate. In the University of Buea, there are about 12,000 students and 973 staff members (500 teachers and 473 administrative /supporting staff. The University of Rwanda (UR), has about 30,445 students and 2,266 staff members (1450 teachers and 816 administrative /supporting) Composition of The study treatments (Artemisia Afra) and control (placebo) will be prepared in the various study and formulations as follows: control Artemisia afra available as infusions containing 5g of Artemisia per liter, will be prepared by adding treatments 5 g dried leaves and twigs of A. afra (in a tea sachet / tea bag) to 1 liter of boiling water, infused for 10 min, and filtered through a sterilized 1 mm mesh. Artemisia afra available as infusions containing 5g of Artemisia in per 500ml, will be prepared by adding 5 g dried leaves and twigs of A. afra (in a tea sachet / tea bag) to 500ml of boiling water, infused for 10 min, and filtered through a sterilized 1 mm mesh. Flavored Artemisia afra available as infusions containing 5g of flavored Artemisia per liter, will be prepared by adding 5 g of flavored dried leaves and twigs of A. afra (in a tea sachet / tea bag) to 1 liter of boiling water, infused for 10 min, and filtered through a sterilized 1 mm mesh. Flavored Artemisia afra available as infusions containing 5g of flavored Artemisia per 500ml, will be prepared by adding 5 g of flavored dried leaves and twigs of A. afra (in a tea sachet / tea bag) to 500mls of boiling water, infused for 10 min, and filtered through a sterilized 1 mm mesh. Flavored placebo available as infusions containing flavored inactive substance per liter, will be prepared by adding flavored inactive substance (in a tea sachet / tea bag) to 1 liter of boiling water, infused for 10 min, and filtered through a sterilized 1 mm mesh. Regular tea placebo will be any tea of choice routinely taken by the selected participants. After preparation, the following doses will be obtained for consumption by participants with

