5.2 Community permission

After obtaining ethical and regulatory approvals, meetings will be held with representatives of participating University communities following specific site procedures, during which the study will be explained in detail (including the objectives, procedures, and implications to the participants) and the study team will answer any questions and concerns raised. The community leaders would review the information and confirm their permission for the conduct of the study. A communique for the study will then be put up in collaboration with the communication department of each University, bearing the precise study period and a reference contact for further clarifications.

5.3 Recruitment: During the baseline visit at the site health stations on Day 0, informed individuals will be invited to participate in a screening and cohort survey on asymptomatic malaria. After informed

consent is obtained, baseline assessments will be carried out and information obtained on participant's sociodemographic characteristics, clinical/medical history, physical assessment, prior medications and contact details. This will be followed by malaria screening tests and participants who fulfil the inclusion criteria will be enrolled in study.

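### The consent sequence contradicts itself: TG8 is to be randomised uninformed while all participants are promised full information first, and people who decline after randomisation are moved into TG8

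*Protocol*

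**What the plan says.** Two sets of statements govern what a participant knows when randomised.

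**The two-step scheme** (Synopsis, study design and study procedures; Section 3, Study Design and Study description). Study Design says: "In the first step, there is an informed consent from all participants for a cohort lifestyle study". It adds that, on this consent, "participants are randomized without knowledge about the detailed protocol". Study description then says that "only participants from the intervention groups (TG1- to -TG7) will receive the information about the intervention and a second consent will be obtained from them". TG8, the regular-tea arm, is therefore not told. Anyone who declines at the second step continues as a control, and Study description names that group as TG8.

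**The general consent rules** (Synopsis and Section 3, Written informed consent; Section 3, Ethical considerations; Sections 5.4 and 10.3). Section 3 requires written consent ahead of any study procedure or treatment and says: "Participants will first be informed about the aim of the study, designs, potential gain, and their right to stop at any moment". The ethics paragraph gives every study participant a clear and detailed explanation. Section 5.4 requires enough understanding of the research, its risks and its benefits for an informed decision. Section 10.3 requires that participants be told everything pertinent, with written consent before inclusion or any study-related procedure. None of these mentions two steps or an exception for TG8.

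The first-step study is also described in two ways: a lifestyle cohort in Study Design, and a screening and cohort survey on asymptomatic malaria in Study description.

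**The concern.** Screening, blood sampling and randomisation are study procedures. Read at face value, the general rules put disclosure of the design before them, while the two-step scheme puts disclosure after randomisation and withholds it from TG8 altogether. The protocol does not say which prevails.

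Two things are at stake. First, the control condition. A site that follows the general rules has a TG8 that knows of the other arms; a site that follows the two-step scheme does not. With two sites and 4 people per site in TG8, awareness could then differ by site within a very small arm.

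Second, comparability. Everyone in TG1 to TG7 decides about the intervention after allocation, and decliners are added to a randomised control arm. They join by choice, so the enlarged TG8 is no longer a randomised group. This second problem comes from the Zelen order and the rule for decliners, not from the contradiction, but the same amendment can settle both.

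**Working it through.** **1. The plan's own total.** Section 8.1 gives 8 per arm in six active arms and 4 per arm in two control arms, at each of two sites.
- Per site: 6 × 8 + 2 × 4 = 56.
- Both sites: 2 × 56 = 112. This reproduces the stated total.

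**2. Who is asked after randomisation.** Study description names TG1 to TG7.
- TG1 to TG7: (6 × 8 + 4) × 2 = 104, and 104 / 112 = 92.9%.
- TG8: 4 × 2 = 8, and 8 / 112 = 7.1%.

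The 104 is the number who can decline, not the number expected to.

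**3. Effect on TG8 if decliners are placed there.** The protocol gives no refusal rate, so r is an assumption. Decliners = 104r; enlarged TG8 = 8 + 104r; share of decliners = 104r / (8 + 104r).

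| Assumed r | Decliners | Enlarged TG8 | Share who are decliners |
|---|---|---|---|
| 5% | 5.2 | 13.2 | 39% |
| 10% | 10.4 | 18.4 | 57% |
| 20% | 20.8 | 28.8 | 72% |

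Decliners equal the 8 randomised members when r = 8 / 104 = 7.7%.

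**4. The two sets of rules side by side.**

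| Question | Two-step scheme | General consent rules |
|---|---|---|
| What does the first consent cover? | A cohort, described in two ways | Aim, designs, potential gain, all pertinent aspects |
| When is the intervention disclosed? | After randomisation | Not separated; consent precedes any procedure |
| Who is told? | TG1 to TG7 | All participants, no exception stated |

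The third row is the clearest conflict. TG8 members are study participants, and they cannot both receive all pertinent aspects of the study and be denied the information about the intervention.

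**5. Where decliners would be analysed.** Section 8.2 does not settle this. The safety population is analysed by treatment actually received, which points to TG8. The full analysis population does not say which arm they belong to. The per-protocol population, which is primary for efficacy, requires all doses as randomised; read literally, that removes decliners from their own arm and gives them no place in TG8.

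**The case against.** The strongest reply is that the two-step scheme can satisfy the timing rule. The first consent is taken on day 0 before assessments and blood sampling, and the second before treatment. The aim and designs explained first could be those of the cohort survey. The consent forms are not in the text reviewed, so what the first form discloses cannot be checked.

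This stands in part, and it rules out saying that compliance is impossible. It does not remove the conflict. The Section 3 consent paragraph speaks of treatment and potential gain, the ethics paragraph covers all study participants, and Section 10.3 requires all pertinent aspects. None of them limits itself to the cohort.

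It is also fair to say that the 104 and the refusal table do not measure the contradiction. They follow from asking after randomisation and would be the same if every consent paragraph agreed. The case for moving consent ahead of randomisation rests on them; the case for reconciling the text does not.

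A reader might go further and infer that everyone is told about the tea before randomisation. No section says so.
- The exclusion criterion "To have a known hypersensitivity to any ingredients of the tea" hints at it, but medical history is taken before randomisation anyway and could reveal a known hypersensitivity without describing the trial.
- Section 5.2 says "the study will be explained in detail (including the objectives, procedures, and implications to the participants", but in meetings with community representatives; the notice that follows is described only as giving the study period and a contact.
- The teaching on preparation in Section 6.2 comes after allocation.

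A reader might also infer that the Zelen design has lost its only benefit. The protocol gives no reason for choosing that design, and the loss would follow only if full disclosure were in fact made before randomisation.

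**Conclusion.** The point holds as a contradiction between the two-step scheme and the general consent rules, joined to a rule that adds self-selected people to a randomised control arm. What TG8 knows at randomisation is undefined, and the sites can differ.

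The firm figures are 104 of 112 asked after randomisation, as a ceiling, and 8 randomised to TG8. The 5 to 21 decliners, and their 39% to 72% share of the enlarged arm, rest on an assumed refusal of 5% to 20% and on decliners being counted in TG8 as Study description says. If the per-protocol definition is applied literally, they leave the primary efficacy analysis instead. TG8 is then not diluted, but the active arms and TG7 lose people by choice after allocation.

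Later analysis cannot establish what TG8 members were told, so this should be settled before the first participant is randomised.

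**What to change.** Use one sequence in the Synopsis (design, consent and study procedures), in Section 3 (Study Design, Study description, Written informed consent, Ethical considerations) and in Section 10.3:

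1. Cohort consent, with a single description of the cohort study.
2. Screening and eligibility.
3. Trial consent describing all arms, from every eligible participant.
4. Randomisation.

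Those who decline at step 3 stay in the cohort unrandomised and are not counted or analysed as TG8. The 56 per site are filled from people who have already agreed. This meets the protocol's own disclosure rule.

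If the sponsor keeps the Zelen order, Section 3 (Written informed consent, Ethical considerations) and Section 10.3 should state exactly what is disclosed before randomisation and that TG8 is exempt from the rest. Decliners should still stay out of TG8 and be analysed in their allocated arm. Section 8.2.3 would then have to say so, because its full analysis population now requires receipt of a study treatment dose.

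**Cost.** An amendment to consent wording and order, with no added visit. The 8 people in TG8 would know that other arms receive Artemisia. Decliners would have to be replaced through more screening. On the Synopsis figures of 635 + 432 = 1,067 rapid tests, the addition is 1,067 / (1 − r) − 1,067, which is about 56 tests at an assumed 5% refusal and 267 at 20%. Under the Zelen order with decliners kept in their arms, no extra screening is needed, but each affected arm contains people who did not take its treatment.

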8.2 Analysis Populations

- **8.2.1 Enrolled Population:** All screened participants who provide informed consent and receive a participant ID, regardless of the participant's randomization and treatment status in the trial.
- **8.2.2 Exposed Population:** All participants in the enrolled population who receive a treatment dose.
- **8.2.3 Trial Populations:** Treatment trial analyses will be performed on both the Full Analysis (FA) Population and Per Protocol (PP) Population.

Full Analysis Population: All participants in the enrolled population who were randomized, received a study treatment dose, and provided an evaluable blood sample at least at one time point post-treatment. Per Protocol Population: All participants in the FA Population who correctly received all doses of study treatment per randomization with no major protocol violations that are determined to potentially interfere with the reactivity assessment of the study treatment. This population will serve as the primary analysis population for all efficacy objectives. Due to unpredictability of some irregularities, the criteria for exclusion of participants from the Per Protocol Population will be determined before the database is locked and will be based on the blind review of protocol violations.

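### The primary efficacy analysis does not compare the groups as randomised: it rests on a per-protocol set, and the plan leaves open where participants who refuse their allocated tea are counted

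*Protocol*

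**What the plan says.** **Consent and allocation.** Under the adapted Zelen design in section 3, "participants are randomized without knowledge about the detailed protocol". Once allocation is done, TG1–TG7 alone are told about the tea and asked to consent again. The study description then says that those who "decline to participate to an intervention will continue in the cohort study, as a control group on regular tea (TG 8". The Study Design paragraph puts it more loosely: "The participants who will decline to participate to an intervention will continue in the cohort study, as the control group".

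**Analysis sets.** Section 8.2.3 names two sets for the trial analyses.

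- Full Analysis: enrolled participants "who were randomized, received a study treatment dose, and provided an evaluable blood sample at least at one time point post-treatment".
- The second set, Per Protocol: members of the Full Analysis set who have "correctly received all doses of study treatment per randomization with no major protocol violations". Of this set the protocol says: "This population will serve as the primary analysis population for all efficacy objectives".

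No efficacy set contains all randomised participants. Analysis by treatment actually received is stated only for the Safety Population (section 8.2.4). The Full Analysis definition does not say in which arm a participant is analysed.

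**Status of this text.** Section 9.4 identifies the pre-specified analysis plan with sections 8.2 and 8.3, so the populations are fixed here. Section 8.3 plans between-group comparisons at P < 0.05.

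**The concern.** Randomisation protects a comparison only if people are analysed where they were allocated. Here two events after allocation decide who counts: accepting the second consent and completing every dose. Neither works the same way in TG8 as elsewhere. TG8 is not asked for a second consent, and its tea is taken at will, so a participant there can hardly fail on dosing.

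Completion may also differ among the other arms, because they differ in flavour, drinks per day and duration of treatment. Adherence and completion are a listed secondary outcome. Making efficacy conditional on completion therefore hides part of the trade-off between activity and acceptability that the primary objective in section 2.3.1 sets out to find.

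If decliners are also moved into the control group, TG8 becomes a mixture of a few people randomised to it and others who selected themselves. A difference between an active arm and TG8 would then reflect who accepts and finishes a tea as well as what the tea does.

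**Working it through.** **1. Arm sizes (sections 3 and 8.1).** Per site: 6 × 8 + 2 × 4 = 56; two sites: 112. Both match the protocol. Asked for the second consent (TG1–TG7): 6 × 8 + 4 = 52 per site, 104 overall. Randomised to TG8: 4 per site, 8 overall.

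**2. Where does a decliner go?** Take someone randomised to TG2 who refuses and drinks regular tea.

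- Section 3 places this person in the TG8 control group.
- Section 8.2.3, Per Protocol, requires all doses as randomised, so this person is excluded.
- Section 8.2.3, Full Analysis, requires a study treatment dose. Whether regular tea counts as one for this person, and in which arm, is not stated.

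Two readings are possible, and the protocol does not choose between them.

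**3. Reading A: decliners counted in TG8.** With refusal rate d (assumed), the share of TG8 randomised elsewhere is 104d / (8 + 104d).

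| d | Decliners | TG8 size | Share randomised elsewhere |
|---|---|---|---|
| 5% | 5.2 | 13.2 | 39% |
| 10% | 10.4 | 18.4 | 57% |
| 20% | 20.8 | 28.8 | 72% |
| 30% | 31.2 | 39.2 | 80% |

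To illustrate the effect on a contrast, assume no treatment effect, 40% response in acceptors and 20% in decliners. People randomised to TG8 respond at m = 0.40(1 − d) + 0.20d. The mixed TG8 responds at (8m + 104d × 0.20) / (8 + 104d).

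- d = 10%: m = 0.38; TG8 = (3.04 + 2.08) / 18.4 = 0.278; false difference 0.40 − 0.278 = 12 points.
- d = 20%: m = 0.36; TG8 = (2.88 + 4.16) / 28.8 = 0.244; false difference 16 points.
- d = 30%: m = 0.34; TG8 = (2.72 + 6.24) / 39.2 = 0.229; false difference 17 points.

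In a null simulation (4,000 runs, pooled active arms against TG8, two-sided Fisher test at 0.05), these settings rejected in 12%, 28% and 39% of runs. Analysed as randomised, they rejected in 3.1%, 2.4% and 3.5%. If decliners respond at 60%, the bias has the same size and the opposite sign. If they respond like acceptors, rejection stays near 4%.

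**4. Reading B: decliners dropped.** TG8 keeps its 8 randomised participants. With the same assumed rates, the false difference is 0.40 − m = 0.20d, that is 2, 4 and 6 points at 10%, 20% and 30%. The same product applies to dose-completion exclusions: excluded share (10–30%) × 20 points = 2–6 points. For refusal alone, simulated rejection was 3.2%, 3.0% and 4.2%, close to the as-randomised figures.

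**5. Contrasts among TG1–TG7.** The Blinding paragraph in section 3 keeps intervention-arm participants unaware of which treatment they have. If refusal does not depend on the arm, the consent step leaves TG1–TG7 comparable with one another. What remains for these contrasts is exclusion for incomplete dosing or major violations, which can differ by arm once the tea is being drunk.

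**The case against.** A reader might infer that 57–72% of the control group in the primary analysis would be non-randomised. The documents do not support that. The Per Protocol definition requires doses as randomised, which excludes decliners, and section 3 describes consent and follow-up without stating an analysis rule. Those percentages arise only if the wording in section 3 governs the analysis. This objection stands, and it leaves an unreconciled conflict rather than a settled contamination.

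A reader might also infer that refusal depends on taste, number of drinks or duration. That is not established either. Participants do not know their treatment, taste is unknown before drinking, and the protocol does not say that arm-specific schedules are disclosed at the second consent. This stands too, and it confines the consent problem to contrasts with TG8.

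Three further arguments carry less weight.

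- *The bias is small.* With 16 people per active arm over both sites, one participant is 6.25 points, more than the 2–6 points under reading B. Supervised intake (section 6.2) may keep missed doses few, and TG7 loses its own non-completers, which could offset part of the bias. All this is fair, but a systematic error does not shrink when arms are pooled: over 96 active participants, one person is about 1 point.
- *Full Analysis is also planned.* It is not primary, and it too requires a dose and a post-treatment sample.
- *This is a pilot without a formal sample size calculation.* Section 8.3 nevertheless compares groups at P < 0.05, and choosing among the arms is the primary objective.

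**Conclusion.** The point holds in this form: on either reading, the primary efficacy comparison is not between the groups as randomised, and sections 3 and 8.2 disagree about where decliners belong.

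The size depends on the reading. If decliners are counted in TG8, more than half of that arm was randomised elsewhere at 10% refusal, and the illustrated false difference is 12–17 points at 10–30% refusal. If they are dropped, the bias is about 2–6 points and the false-positive rate hardly moves in the refusal simulation. Refusal rates, exclusion shares and response rates are all assumptions, since the protocol gives none; the sign reverses if decliners respond better than acceptors.

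Contrasts with TG8 are affected by both consent and completion. Contrasts among TG1–TG7, including those with the flavoured placebo, are exposed mainly through dose-completion exclusions.

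**What to change.** In sections 3 and 8.2, and in the matching synopsis text:

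- Define the primary efficacy population as all randomised participants, analysed in the allocated arm whatever their second-consent decision or adherence.
- State that only participants randomised to TG8 are counted in TG8. Decliners may continue in the cohort, but for analysis they stay in their allocated arm and are reported there as a separate row.
- Make the per-protocol and as-treated analyses supportive.

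The cost is wording. Decliners already remain in the cohort, and section 6.4 encourages people who stop treatment to stay until Visit 5, so most outcomes should exist without extra visits or samples. The downside is that active-arm estimates are somewhat diluted by decliners and non-adherers; the supportive per-protocol analysis still shows the result in those who completed treatment.
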